1.1. Executive Summary

An estimated 7.7 million pre-school aged children die each year, the majority from infectious diseases.¹ Mass azithromycin distributions for trachoma may have the unintended benefit of reducing childhood mortality.¹ We recently demonstrated the biannual mass azithromycin distribution significantly reduces all-cause child mortality in a cluster randomized trial (MORDOR I) conducted in three diverse regions of Sub-Saharan Africa.²

Our long-term goal is to more precisely define the role of mass azithromycin treatments as an intervention for reducing childhood morbidity and mortality. We propose a cluster randomized trial designed to repeat the original study to confirm the original results in a different geographic study with similarly high child mortality, and to better understand the mechanism behind any effect of azithromycin on child mortality.

1.2. Objectives

- 1: Determine the efficacy of biannual mass azithromycin distribution versus placebo in children aged 1-59 months for reduction in all-cause mortality. *We hypothesize that biannual distribution of azithromycin will lead to significantly reduced all-cause mortality among children aged 1-59 months after 36 months of treatment.*
- 2: Determine the efficacy of targeted azithromycin distribution to infants during an early infant healthcare visit (approximately 5th through 12th week of life) on infant mortality. *We hypothesize that infants receiving a single dose of azithromycin during early post-neonatal infancy will have significantly lower all-cause mortality compared to infants receiving placebo.*
- 3: Determine the mechanism behind the effect of biannual mass azithromycin distribution for reduction in child mortality.

1.3. Study Partners

This study was jointly designed and will be jointly implemented by partners at CRSN and UCSF. CRSN and UCSF partners contributed equally to the development of this protocol. Funding for the study is provided by the Bill and Melinda Gates Foundation.

1.4. Study Site

[figure not shown]
The study will be conducted in the Nouna District in northwestern Burkina Faso. It is situated about 300 kilometres north-west of Ouagadougou, the capital of Burkina Faso.

Nouna Health District is one of the six districts of Boucle du Mouhoun Health Region and covers the geographical area of Kossi Province in the western part of the country. Nouna is the capital of Kossi province. The health district comprises of the town of Nouna with a total population of 29,297 inhabitants and a rural area of about 235,426 inhabitants.

The multicultural society consists of 15 ethnic groups whereof the major ones are the Mossi, Bwaba, Marka, Samo, Gourounsi and Peuhl ethnic groups. The main socioeconomic activity of the population in the district is farming, similar to the rest of the country. The only exceptions are the Peuhl who are semi-nomadic cattle herders and dairy producers.

The health infrastructure consists of one District Hospital in Nouna (Centre Medical avec Antenne chirurgicale, CMA), and over 34 dispensaries (Centre de Santé et de Promotion Sociale, CSPS). The District Hospital in Nouna covers a population of 300,360 inhabitants. The Health Centers each cover a total population between 2,195 and 34,581 inhabitants. Due to deficient road infrastructure only 69.13% of health facilities are accessible for the DHMT all over the year with a mean distance of 8.48 kms (Nouna District action plan 2012). Targeted treatment will also be done in the district of K. Vigué in the Haut Bassins region and in the district of Banfora in the Cascades region..

Province de la Kossi
Carte Administrative et Sanitaire

Scale :

1000000 0 1000000 2000000 Kilometers

Autor : [name], SIG-TD CRSN
Source : NIG-GIS
Date : may, 21th 2018

Legend :	
■	HDSS localities
●	District localities
Roads	
■	National
—	Regional
—	Communal
.....	track
■	HDSS Area
■	District Area
□	Communes boundaries

4 Chapter 2: Context

Although child health and mortality are improving worldwide, children in the Sahel and sub-Saharan regions of West Africa have the greatest risks of mortality.^{4,5} Burkina Faso's current under-5 mortality rate is estimated 110 per 1,000 live births⁴. Similar to other countries in the region, the major causes of child mortality in Burkina Faso are malaria, respiratory tract infection, and diarrhea. Malnutrition acts as a major underlying contributor to mortality.^{6,7} Interventions that address these underlying causes may be particularly efficacious for reducing mortality.

Younger children are at a higher risk of mortality. Approximately 2/3rd of under-5 deaths occur during the first year of life.⁴ In general, the child mortality rate decreases as age increases. While some improvement has been observed, neonatal mortality is declining at a slower rate than post-neonatal childhood mortality.⁴ Many child health interventions are designed specifically for children over 6 months of age, such as vitamin A supplementation, seasonal malaria chemoprevention, and lipid-based nutritional supplementation. Identification of strategies that are safe and effective for the youngest children will be required to address persistently high rates of neonatal and infant mortality.

The MORDOR I study demonstrated a significant reduction in all-cause child mortality following biannual mass azithromycin distribution. Across three diverse geographic locations in sub-Saharan Africa (Malawi, Niger, and Tanzania), biannual mass azithromycin distribution over a two-year period led to a 14% decrease in all-cause child mortality. In Niger, 1 in 5-6 deaths were averted. These results are qualitatively similar to those of a previous study of mass azithromycin distribution for trachoma control in Ethiopia, which found reduced odds of all-cause mortality in children in communities receiving mass azithromycin compared to control communities.¹

In MORDOR I, the strongest effect of azithromycin was in the youngest cohort of children. Across all three countries, the strongest effect of azithromycin was consistently in children 1-5 months of age, with an approximately 25% reduction in all-cause mortality. However, MORDOR I was not optimized to target the youngest age groups. Although children as young as 1 month were eligible, biannual distributions might not reach some children until 7 months of age. On average, children were first treated at 4 months. Given that there may be a substantial benefit to treating children at younger ages, azithromycin strategies

that are designed to target younger age groups may be even more beneficial for reducing child mortality.

Here, we propose a randomized controlled trial designed to evaluate the efficacy of mass and targeted azithromycin strategies for child mortality. In the rural northwestern district of Nouna in Burkina Faso, we propose to randomize villages to biannual mass azithromycin distribution or placebo. This study was designed by CRSN and UCSF partners to confirm the results of MORDOR I, evaluate an alternative health systems distribution point (targeted treatment) for delivery of azithromycin to young children, and to provide a platform for evaluation of potential mechanisms behind the effect of azithromycin by collecting and processing additional specimens and tests.

5 Chapter 3: Study Design

[figure not shown]
The research team will assess childhood mortality over three years, comparing communities where children aged 1-59 months receive biannual oral azithromycin and/or targeted azithromycin during the 5th-12th week of life in conjunction with the first Expanded Programme on Immunization (EPI) vaccine visit, the BCG vaccine visit and the 42-day postnatal health visit/well-child visit or biannual placebo and targeted placebo. All eligible communities in Nouna District will be randomized (278 communities). A random sample of 48 (24/arm) communities from within the HDSS will be selected to participate in the “Mortality Plus” study, which will entail an annual morbidity exam among 15 randomly selected children per community to monitor infectious disease morbidity, nutritional status, and macrolide resistance. All communities will contribute to the mortality outcome. All biologic specimens collected as part of the morbidity and resistance outcomes will be stored and made available to other investigators for further laboratory testing at the conclusion of the study, per Gates Foundation guidelines.

3.1. Randomization

Randomization of Treatment Allocation. All eligible communities in Nouna District will be randomized in a 1:1 fashion to biannual azithromycin or placebo. Targeted treatment will be randomized 1:1 individually to azithromycin or placebo in the nouna, K vigué and banfora districts. Refer to SAP for randomization details.

Study Participants: At months 0, 12, 24, and 36 a random sample of children will be selected using a computer-generated simple random sample for exams and sample collection to monitor for morbidity and resistance in the Mortality Plus communities.

Figure 1: Trial Profile

6 Chapter 4: Study Eligibility

4.1. Eligible Communities

To be eligible for the trial, a community must meet the following criteria:

1. The community location in target district.
2. The community leader consents to participation in the trial (this does not obviate the need for individual consent, but without overall leadership consent, the community as a whole cannot be part of the trial).
3. Eligible communities estimated population no more than 2,000 people.
All communities with an estimated population of more than 2000 people will be split into 2 or more randomization units
4. The community is not in an urban area.

6.1 Eligible Individuals

Mortality Study:

Census: The study can be thought of as consisting of seven 6-month segments, each of which starts with a census and ends with a follow-up census. All children in the study communities aged 1-59 months (up to but not including the 5th birthday) at the initial census of each segment are eligible to participate in the subsequent 6-month segment of the study. Note that the information for children erroneously entered into the census (e.g., children younger than 1 month or \geq 60 months) can be corrected at the subsequent treatment, subsequent census, or at a verbal autopsy later in the study. However, these changes will not be applied retroactively; these misclassified children will still be included in the study population for that 6-month segment and any deaths will be counted toward the primary outcome. In addition, all children listed on the initial census for that 6-month segment will be included in the outcome, regardless of whether they received the study drug.

Treatment: Individuals allergic to macrolides or azalides will not be given the study antibiotic azithromycin, but will be included in the outcome. Children weighing less than 3.8 kg will not be given treatment either.

Birth Notification: All births in all study communities will be recorded over the duration of the study.

Mortality Plus Communities:

Census: The criteria for being included in the census are the same as the Mortality Study, as described above.

Treatment: The inclusion and exclusion criteria for treatment are the same as for the Mortality Study, as described above.

Examination & Sample Collection: A random sample of children aged 1-59 months (up to but not including the 5th birthday) are eligible for examination and sample collection. As described above, the random sample will be a simple random sample based on the previous census. These individuals will likewise be selected from the previous census.

4.2. Study Schedule

The schedule for examination and treatment is shown below in Table 1:
MORDOR II Study Schedule

	MORTALITY	MORTALITY PLUS
Ongoing	Birth notification 1 st EPI or BCG or 42-day postnatal visit/well-child visit azithro or placebo 6 mo vital status 6 mo Anthropometry assessments	Birth notification 1 st EPI or BCG or 42-day post natal/well-child visit azithro or placebo 6 mo vital status 6 mo Anthropometry assessments
MORDOR 0 Aug-19 to Jan-19	Census Azithro or placebo	Census Swabs Blood Anthropometry Azithro or placebo
MORDOR 6 Feb-19 to Jul-20	Census Verbal Autopsy Azithro or placebo	Census Azithro or placebo
MORDOR 12 Aug-20 to Jan-20	Census Verbal Autopsy Azithro or placebo	Census Azithro or placebo
MORDOR 18 Feb-20 to Jul-21	Census Verbal Autopsy Azithro or placebo	Census Azithro or placebo
MORDOR 24 Aug-21 to Jan-21	Census Verbal Autopsy Azithro or placebo	Census Azithro or placebo
MORDOR 30 Feb-21 to Jul-22	Census Verbal Autopsy Azithro or placebo	Census Azithro or placebo
MORDOR 36 Feb-22 to Jul-22	Census Verbal Autopsy Azithromycin for all Birth History (subset of communities)	Census Swabs Blood RDT Anthropometry Swab targeted treatment group
Note: Only children aged 1 month to 59 months in each community will be treated during mass drug administration		

7 Chapter 5: Core and Non-Core Study Elements

An overview of core and non-core elements for the mortality and morbidity study is provided here, but will be described in more detail in the following chapters.

5.1. Mortality Study - All Communities

5.1.1. Core Elements

We will conduct the following study activities for the mortality study:

Training

Standardization activities before each biannual census will consist of didactic classroom instruction and mock census activities, followed by in-field training.

Pre-census and mapping questionnaire

Before the beginning of the study, we will perform a pre-census to be able to list all compounds and household in our study area. This pre-census will help us organize our data census collection by knowing the area we will be working on.

The pre-census will include all questions ask during regular census (see chapter census below) and will include a mapping questionnaire about the characteristics of each household:

- Wall, roof and ground of the house
- Type of water supply
- Latrinization
- Electricity
- Telephone (if exist take number with permission)
- Cooking
- Education of the head of household and mother/guardian
- Child individual information:
 - o Pre schooling
 - o Breastfeeding
 - o Use of bednet
 - o Handicap

Census

An enumerated population census for 0 – 60 month olds (focusing on this age group) will be conducted every 6 months by trained field workers masked to study arm, recording births, deaths, and migration of children eligible for treatment. Pregnant

women will be noted at each census, to maximize inclusion of newborns on the subsequent census.

Core Census Elements

The following elements will be considered part of the core HDSS census activities:

- Enumeration of the compound
- Full enumeration of household members with emphasis on children aged 0-60 months (age, sex) in a way that each child could be linked to his mother
- Enumeration of pregnancies
- Recording of caregiver for each child <60 months
- Recording head of household
- Mid-upper arm circumference measurement for all children aged 0-60 months
- GPS coordinates

Random Census Verification

A repeat census will be conducted in a random selection of households at each study visit. Personnel will be different from the original census. This will allow us to assess whether the census identified all births, deaths, and migratory episodes relative to the previous census.

Verbal Autopsy

Verbal autopsy will be conducted in the district according to current methods for measuring verbal autopsy for all children aged 1-59 months who died during the study.³ The interview is conducted with the caregivers or relatives, using the WHO standard verbal autopsy questionnaire WHO-VA-2016. The interview usually takes place two months after the event with the person who assisted the deceased before the death. The data collected will be coded using InterVA 4.

Treatment

Children aged 1-59 months on the current census will be offered weight- or height-based (<1 year and older children who can't stand will be weighted; ≥1 year will be measured with a flexible dosing stick), directly observed, oral azithromycin suspension (or oral placebo) every 6 months for 3 years as performed in trachoma programs. Specifically, individuals are eligible on or after their one month birthday, and prior to the day of their fifth birthday.

At the final treatment distribution, CHAT 36, all children 1-59 months old will be given a single dose of azithromycin. Placebo will not be utilized at the final phase.

Antibiotic Coverage Surveillance

We will estimate antibiotic coverage from the most recent biannual census records. At the end of each treatment round at months 6, 12, 18, 24, and 30 we will identify any children who have missed 2 or more consecutive treatments, and forward this information to the census team.

Birth history at the 36 months visit

At the final visit (36 month) we will obtain birth history in a subset of communities. All women in childbearing age living in selected communities will be asked if they experienced births in the last 10 years. Name of women, age, name of children and age or date of birth will be collected. Vital status of each birth will be recorded.

5.2. Mortality Plus Communities

5.2.1. Core Elements

All core elements described in 5.1.1 will also be conducted in the Mortality Plus communities.

The designation “core elements” means that all study communities will be performing the study activity.

In all study sites, we will perform the following tests on a random sample of 15 children aged 1-60 months from each community at baseline, 12, 24, and 36 months:

- Blood samples (dried blood spots) for malaria and anemia
- Nasopharyngeal swabs for pneumococcal macrolide resistance
- Stool samples or rectal swabs to assess for macrolide resistance
- Anthropometric assessments
- Rapid diagnostic test for malaria (at 36 months only)

Samples will be processed at the CRSN laboratory for microbiological culture, targeted PCR, serologic, thin and thick smears, and ova and parasite tests. Samples for microbiome analyses and specialized tests required by the Gates Foundation will be shipped to the United States.

At the final visit (36 months), in the mortality plus communities, we will obtain one rectal swab from up to 10 children per community who participated in the targeted treatment distribution.

5.2.2. Non-core Study Elements

The designation “non-core” element means that not all study communities will be participating in the activity.

Mother MUAC assessment

In a subset of 20 villages, we will train mothers/guardians on measuring MUAC on their children weekly. We will train mothers/guardians to bring children to the nearest CSPS for evaluation if MUAC is <125mm.

Passive Surveillance

In each Centre de Santé et de Promotion Sociale (CSPS, community health facility), we will conduct morbidity passive surveillance. Each CSPS will be equipped with a tablet for electronic capture of health facility visits. Each visit will be recorded, including the reason for the visit (e.g., fever, diarrhea, malnutrition, etc), the village of residence, the person’s age and sex, diagnosis (e.g., malaria, pneumonia, etc), treatment (e.g., antibiotic, antimalarial, etc), and timing of the visit (e.g., first versus follow-up visit). Note that this data is already routinely collected on paper forms. Identifying information like names will not be collected.

In each CSPS included in the Mother MUAC assessment, we will collect data on malnutrition including name of participants in the program, study ID, village of residence, date of admission in the program, measurements of weight and height, treatment received and outcome. Notes that this data is already collected on paper forms

Passive surveillance in the district hospitals located in our study area: we will collect study ID, name of participant, village of residence, date of admission and discharge, reason for hospitalization, treatment, and outcome of hospitalization for all children hospitalized under 6 months of age. Notes that this data is already collected on paper forms

7.1 5.3 Individually randomized targeted treatment

Recruitment

There are three occasions in which children could be recruited for the targeted treatment:

- 1) During the 1st BCG visit at approximately 5 weeks of life if the child is at least 29 days old.
- 2) During the 6 week (42 days) postnatal follow-up visit or any other well-child visit happening during the age of 5 weeks to 12 weeks
- 3) When children are attending their first EPI vaccine visit at approximately 12 weeks of life (1st EPI vaccine visit).

Enrollment

The children will be enrolled for targeted treatment at the health center or during other health outreach in the community after obtaining written consent from at least one guardian. Enrollment will happen at the Nouna district, the K. Vigué district and Banfora districts

The children enrolled have to be living in a participating study community and be aged 28 days to 12 weeks.

Anthropometric Baseline assessments

All children enrolled in the study will undergo anthropometry: we will measure height, weight and middle arm circumference of each child.

Treatment

In all communities, children attending local health posts or children present at community health outreach will have the opportunity to receive a dose of azithromycin or placebo. Children will be individually randomized to receive placebo or azithromycin. Receipt of treatment will be recorded on the child's study card. This treatment will occur whether the targeted treatment occurs during other health outreach or when the caregiver seeks vaccination at the health post or when the child visits the health post for a well-child visit. Community health workers will conduct a household visit when the mother and child do not come to the health post.

2-week infant adverse event survey

To identify any adverse events associated with the individually treated children, the research team will perform an adverse event survey approximatively 2 weeks after the treatment has been administered in a random subset of children. 10% of the children treated as part of the study will be randomly selected and the 2-week IAES will be performed. This survey will be performed by the census workers masked to treatment arm. A structured questionnaire will be performed to elicit adverse events following treatment, followed by an open-ended question. Specifically, we will ask the primary caregiver about the following

symptoms during the time since the previous antibiotic distribution: abdominal pain, vomiting, diarrhea, constipation, hemorrhoids or rash.

Six-month Mortality

All children treated in all study communities will be followed for 6 months for vital status assessment. At approximately 6 months of age, a field worker will assess the vital status of the child (alive, died, unknown) and their current residence (residing in the household, moved, unknown). This visit will be an in-person visit to the health post.

Six-month Anthropometry assessment

All children treated during the targeted treatment visit in all study communities will be followed for anthropometry assessments at approximately 6 months of age. The child will be measured, weighted and we will measure the middle upper arm circumference. This procedure will be done at the health post during the 6-month old vaccine visit.

Rectal swab collection

During the 36 months visit in the mortality plus communities we will obtain one rectal swab from up to 10 children per community who participated in the targeted treatment.

8 Chapter 6: Census

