11.4 Catalog Specimens

We will create a list of study data and specimens, including the age, gender, village identification number, treatment assignment, whether treatment was received, vaccination record, and symptom questionnaire. We will also list the date of collection and transport, and the storage conditions while in the field and while banked at UCSF. This will facilitate identification of specimens for future analyses.

11 Chapter 12: Study Medication

Children aged 1-59 months on the current census will be offered weight- or height-based, directly observed, oral suspension (azithromycin or placebo) every 6 months for 3 years (as performed in trachoma programs) at each study site. At the final phase of CHAT, all children 1-59 months will be offered azithromycin. Children under the age of 12 months or not able to stand will be weighted. In addition to being at least 1 month of age, children should weigh at least 3.8 kg to be eligible for treatment. This ensures that mistakenly aged or premature infants won't be treated. These infants will be eligible for treatment at the subsequent distribution, approximately 6 months later. The mortality application will not provide a dose for children weighing <3.8 kg.

We will monitor adverse events following mass treatments as described in the adverse events section. The treatment and monitoring schedule for all study arms is shown in Table 1.

11.1 12.1 Study Medication Description (from Pfizer, Inc.)

Azithromycin

Zithromax® for oral suspension is supplied in bottles containing azithromycin dehydrate powder equivalent to 1200mg per bottle and the following inactive ingredients: sucrose; tribasic anhydrous sodium phosphate; hydroxypropyl cellulose; xanthan gum; FD&C Red #40; and flavoring including spray dried artificial cherry, crème de vanilla, and banana. After constitution, a 5mL suspension contains 200mg of azithromycin.

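### The protocol does not say whether Chapter 12's age and weight conditions for treatment (1 month, 3.8 kg) apply to the targeted infant dose, and Section 5.3 follows only treated infants

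*Protocol*

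**What the plan says.** Protocol Section 5.3 (Enrollment) admits infants to targeted treatment on residence and age: "The children enrolled have to be living in a participating study community and be aged 28 days to 12 weeks". The Recruitment list in the same section gives a different lower age for one route: "During the 1st BCG visit at approximately 5 weeks of life if the child is at least 29 days old". Objective 2 (Section 1.2) describes the window as "approximately 5th through 12th week of life". At baseline, "we will measure height, weight and middle arm circumference of each child", but no rule in Section 5.3 uses the weight.

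Chapter 12 (Study Medication) says: "In addition to being at least 1 month of age, children should weigh at least 3.8 kg to be eligible for treatment". Its reason is: "This ensures that mistakenly aged or premature infants won't be treated". For those below the floor: "These infants will be eligible for treatment at the subsequent distribution, approximately 6 months later". It adds that the mortality application withholds a dose below 3.8 kg. The weight floor is repeated under Eligible Individuals in Chapter 4, within the Mortality Study paragraph.

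For follow-up, Section 5.3 says: "All children treated in all study communities will be followed for 6 months for vital status assessment". The 6-month anthropometry visit is likewise limited to children who were treated.

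**The concern.** Section 5.3 recruits the youngest infants in the study. Chapter 12 withholds treatment from infants who are too light, for a reason that concerns the infant (prematurity or a wrong age) and not the way the dose is delivered. Section 5.3 does not repeat that condition, waive it or refer to it.

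Two things are at stake. The first is consistency: field staff following one passage or the other would give different answers for the same low-weight infant. The second is the randomized comparison for Objective 2. If a weight condition takes effect after the allocation is drawn, some randomized infants will be untreated, and Section 5.3 schedules no vital-status or anthropometry visit for them. Infants of low weight are plausibly at higher risk of death, so losing them could matter for a mortality endpoint.

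**Working it through.** The plan states no figure to reproduce here. The check is mainly a comparison of passages, with a little arithmetic on ages.

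**Step 1. The rules side by side**

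| Item | Section 5.3, targeted dose | Chapter 12, Study Medication |
|---|---|---|
| Age floor | 28 days (Enrollment); 29 days (BCG route) | 1 month |
| Weight floor | None stated; weight is measured | 3.8 kg |
| Infant below the floor | Not addressed | Eligible at the next distribution, about 6 months on |
| Software check | None described | Mortality application gives no dose |

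**Step 2. Does the text fix the scope of Chapter 12?**

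- Cues for mass rounds only: the chapter opens with children on the census treated every 6 months, it speaks of the next distribution, and the repeat of the weight floor sits under the Mortality Study.
- Cues for all study drug: it is the only medication chapter; Section 5.3 has no dose or allergy exclusion of its own, so Section 12.2 is the only source for both; and Chapter 12 points to Table 1 (Section 4.2), which lists the targeted dose.

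No sentence settles it. Section 5.3 has no cross-reference to Chapter 12, and the documents do not say whether targeted visits use the mortality application.

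**Step 3. Consequence of each reading**

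- *Mass rounds only.* An infant past 1 month but under 3.8 kg gets no dose at a mass round and is deferred about 6 months, yet meets the Section 5.3 conditions at a clinic visit soon after. This needs a mass round. Section 3.1 describes community randomization for Nouna alone, so the sequence is limited to Nouna.
- *All study drug.* The same infant satisfies Section 5.3 and can be enrolled and randomized, but may not be dosed. Section 5.3 then follows only treated children. In Nouna the biannual census may still supply vital status. For K. Vigué and Banfora no census is clearly described. Eligible Individuals keeps untreated children in the mass-trial outcome; Section 5.3 has no equivalent sentence.

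**Step 4. Size of the age mismatch**

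- Calendar month minus 28 days: 28, 29, 30 or 31 − 28 = 0 to 3 days. The mean is 365.25/12 − 28 = 30.44 − 28 = 2.44 days.
- Enrolment window, taking 12 weeks as 84 days: 84 − 28 = 56 days. Share of the window below 1 month: 2.44/56 = 4.4% on average, at most 3/56 = 5.4%.
- The 5th week of life begins at 28 completed days, so the 28-day floor agrees with Objective 2. Within Section 5.3 the disagreement is 1 day (28 against 29).

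**Step 5. Could a mass round and a targeted visit fall close together?**

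Assume births spread evenly over time and rounds exactly 365.25/2 = 182.6 days apart. The share of infants in mass-treated communities with a round between 1 month and 12 weeks of age is (84 − 30.44)/182.6 = 29%. From 28 days it is 56/182.6 = 31%. This shows only that the timing is feasible. It is not the share of infants refused at a round.

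**Step 6. How many infants are below 3.8 kg?**

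The documents give no weight distribution for this age group, so the number affected cannot be derived.

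**The case against.** The best defence is that this is silence on scope and not a contradiction. If Chapter 12 covers mass rounds, two interventions simply have two rules. If it covers all study drug, Section 5.3 governs enrolment and Chapter 12 governs dosing, and both can be followed. Section 5.3 also places weighing ahead of the paragraph on randomization, so a check before allocation fits the written order. The community study forms (Appendix 5) are not in the text available, and a weight screen may exist there.

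Much of this stands, and it rules out several stronger readings that a reader might infer:

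- That an infant refused at a mass round can therefore be dosed days later. This follows only if Chapter 12 does not bind the targeted dose, which the text leaves open.
- That the age floor within Section 5.3 varies by a week. The 5-to-12-week phrase describes which well-child visits count as recruitment occasions. It is not a separate eligibility floor.
- That an undosed infant has no outcome at all. The Nouna census may supply vital status; what is missing is the Section 5.3 visit.
- That the targeted route ought to carry a weight limit. The documents do not settle that, and it is a clinical decision.

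The defence does not remove the need for a correction. A reason stated in terms of the infant leaves staff unsure whether it applies to the youngest infants in the study. Weighing before randomization protects nothing unless a rule uses the weight. And restricting follow-up to treated infants leaves a gap in the randomized comparison whenever a randomized infant is not dosed, for whatever reason.

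**Conclusion.** The point holds as an unreconciled scope with a consequence for follow-up. The protocol gives one set of conditions for enrolment in the targeted trial and a stricter set for treatment, and does not say whether the second applies to the first. The age part is minor: 1 day within Section 5.3 and 0 to 3 days against a calendar month. The weight part is the substance, but its size is unknown because it depends on a weight distribution that the documents do not give.

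The missing weight criterion concerns all three districts. The sequence of refusal at a mass round and then a qualifying clinic visit concerns Nouna only. The follow-up gap is likely to matter most in K. Vigué and Banfora, where no census is clearly described. The conclusion assumes that no form or application outside the supplied text already resolves the question. It takes no view on which age or weight rule is right.

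**What to change.** - Reconcile Eligible Individuals (Chapter 4), Section 5.3 (Recruitment and Enrollment) and Chapter 12, so that the protocol states one age window in days for the targeted dose and says explicitly whether the Chapter 12 age and weight conditions apply to it. The content is for the clinical team and the ethics committees.
- Apply whatever eligibility results before the allocation is drawn, at the baseline weighing that Section 5.3 already requires, with a matching check in the enrolment application.
- Change the 6-month vital-status and anthropometry follow-up in Section 5.3 from treated children to all randomized children. This is worth doing under either reading.

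The cost is minor protocol wording, an application check, and follow-up of a few infants who were randomized but not treated. Depending on the reconciliation, an unknown number of infants may become ineligible.
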